**IOP changes from baseline in raw IOP at Weeks 8, 15, and 20**

Week 8, 15 and 20 raw IOP values and their changes from baseline will be descriptively summarized for Bim SR eye and SLT eye at each timepoint.

**10.3 OTHER EFFICACY ANALYSES**

#### 10.4 SENSITIVITY ANALYSES

As part of the sensitivity analyses, the mean difference and 95% CI in the IOP change from baseline between the Bim SR eyes and SLT eyes (Bim SR minus SLT) will be constructed for each analysis visit for the Per Protocol (PP) population using the same MMRM model as the one used in the primary analysis.

To simplify the interpretation of treatment effect, and to allow flexible adjustment for baseline effect and the between-eye correlation across different visits, the following MMRM model will be used in sensitivity analysis using mITT population: (1) the MMRM model will include Hour 0 IOP change from baseline as the response variable and treatment, visit, eye, baseline Hour 0 IOP, treatment-by-visit, visit-by-baseline Hour 0 IOP, and visit-by-eye interactions as covariates; (2) an unstructured covariance matrix (6×6 matrix) will be used for measurements across 3 primary visits (Weeks 4, 12, and 24) and 2 eyes for the same patients. The same MMRM model will be used in the tipping-point sensitivity analysis described in the later part of the section.

Sample SAS® code for the sensitivity analysis is shown as below:

```
proc mixed data=iop4;
  where avisitn >1;
  class subjid eye trt avisitn repid;
  model chg=trt avisitn eye base trt*avisitn
        avisitn*base avisitn*eye/ddfm=kr;
  repeated repid/type=un subject=subjid rcorr;
  lsmeans trt*avisitn/diff;
run;
```

The definitions of variables are:

chg = Hour 0 IOP percentage change from baseline at the primary analysis time points of Week 4, Week 12, and Week 24

avisitn = Programming derived analysis visits at Week 4, Week 12, and Week 24

subjid = Subject ID

eye = Variable to indicate primary eye or contralateral eye

trt = Variable to indicate Bim SR treatment or SLT treatment

base = Baseline IOP

repid=Variable created to identify the repeated measures cross each eye and each visit within a given subject for the unstructured covariance matrix ( $6 \times 6$ ).

Additionally, ANCOVA including within-subject correlation at each visit will be conducted using the observed values of ITT population, where IOP measurements obtained after initiating the use of non-study IOP-lowering medication will be set to missing. At each visit, the model for IOP change from baseline is specified as: IOP Change from Baseline = Treatment + Eye + Baseline IOP, where Eye is primary eye or contralateral eye. A compound symmetric covariance matrix will be used for between eye correlation.

The tipping-point sensitivity analysis will also be used to assess the robustness of the analysis results. A multiple imputation (MI) will be performed to the missing data as the first step; then different shifts using various assumptions on the missing IOP CFB will be applied to the imputed missing values in Bim SR treated eyes separately (note: shift will not be applied to SLT treated eyes); finally MMRM analyses will be conducted based on the imputed data with shifts and the corresponding tipping region of the shifts will be used to evaluate the robustness of the noninferiority conclusion.

In the MI procedures, a two-step method will be used to impute the missing values at Weeks 4, 8, 12, 15, 20, and 24 for each eye. During Step 1, missing intermittent data will be imputed to obtain a monotone missing pattern and during Step 2 linear regression will be used to impute the remaining missing values. Note that baseline IOP values associated with each eye must not be missing in any of the patients; otherwise they will be excluded from this analysis. At least twenty-five (25) sets of imputed datasets will be created using SAS proc MI procedure. A sample code is shown below for Hour 0 IOP measurements associated with each eye:

```
proc mi data=iop nimpute=25 seed=123451 out=_miint;  
  var baseline week4_hr0 week8_hr0 week12_hr0 week15_hr0 week20_hr0 week24_hr0;  
  by treatment;  
  mcmc chain=single impute=monotone;  
run;  
  
proc mi data=_miint nimpute=1 seed=123457 out=mifull;  
  class race_group sex lens;  
  var race_group sex lens age baseline week4_hr0 week8_hr0 week12_hr0 week15_hr0 week20_hr0  
  week24_hr0;  
  monotone regression (week4= race_group sex lens age baseline/details);  
  monotone regression (week8= race_group sex lens age baseline week4/details);  
  monotone regression (week12= race_group sex lens age baseline week4 week8/details);  
  monotone regression (week15= race_group sex lens age baseline week4 week8 week12/details);  
  monotone regression (week20= race_group sex lens age baseline week4 week8 week12 week15/details);  
  monotone regression (week24= race_group sex lens age baseline week4 week8 week12 week15  
  week20/details);  
  by _imputation_ treatment;  
run;
```

MMRM method will be used to analyze each imputation dataset obtained from the above. PROC MIANALYZE will then be used to pool the analyses results across the imputation datasets and produce final parameter estimates.

Additional sensitivity analyses may be conducted to further evaluate the robustness of primary analysis results.

## 11.0 SAFETY ANALYSES

All safety analyses will be performed using the Safety Population. As indicated in [Section 6.5](#), safety data collected at Screening for eligibility assessment will not be analyzed.

Non-ocular safety assessments include: non-ocular adverse events (AEs), clinical laboratory, vital signs (blood pressure, pulse rate and temperature), and pregnancy test. Ocular safety will be evaluated through: ocular AEs, best corrected visual acuity, visual field examination, specular microscopy, macroscopic iris color assessment, macroscopic conjunctival hyperemia assessment, gonioscopy / angle assessment, biomicroscopy (using a slit lamp), lens assessment, optic disc examination, dilated ophthalmoscopy, pachymetry, and anterior segment-optical coherence tomography.

[REDACTED]

Unless otherwise stated, the last non-missing safety assessment before the SLT treatment (Day 1) will be used as the baseline for all analyses of that safety parameter.

Analysis study periods are defined as follows:

- **During the study:** Date of SLT treatment through Week 52/Exit visit/last study visit available.
- **Analysis Cycle 1:** SLT Treatment date (Day 1) through the second Bim SR implant date – 1. If the second Bim SR implant was not given to a patient, all safety assessments through Week52/Exit visit/last study visit available will be included in analysis cycle1.
- **Analysis Cycle 2:** Second Bim SR implant date through the third Bim SR implant date – 1. If the third Bim SR implant was not given to a patient, all safety assessments through Week52/Exit visit/last study visit available will be included in analysis cycle 2.
- **Analysis Cycle 3:** Third Bim SR implant date through Week 52/Exit visit/last study visit available. Note that only Stage 1 patients were eligible to receive third Bim SR implant.

All summaries will be based on the first treatment received in each eye (Bim SR or SLT), except one patient who received both SLT and Bim SR in the same eye (Safety assessment will be summarized in Bim SR). For non-ocular safety measures, overall summaries will be presented. For ocular safety assessments, summaries will be presented for the periods of during the study, Analysis Cycle 1, Analysis Cycle 2, and Analysis Cycle 3 as shown in Figure 11-1 below.

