efficacy analysis, and allows for assessment of the duration of effect of 2 Bimatoprost SR administration cycles throughout the study. With the implementation of Amendment 3, Allergan is discontinuing the administration of the Bimatoprost SR 15 µg dose strength to patients based on a thorough review of the long-term Bimatoprost SR safety data from the recently completed and ongoing studies. The discontinuation is based on the conclusion that corneal adverse events associated with repeat administrations of the 15 µg dose strength are no longer supported by a favorable benefit:risk consideration.

The comparator that is to be administered in the contralateral eye is selective laser trabeculoplasty (SLT), which is also indicated for this patient population. SLT, one of the most frequently used LT modalities, is commonly used as an intermediate step between topical medications and incisional glaucoma surgery and is comparable in efficacy and durability to argon laser trabeculoplasty (ALT) (Damji et al, 1999; Damji et al, 2006; Martinez-de-la-casa et al, 2004; Rolim de Moura et al, 2007; Wang et al, 2013). SLT causes minimal tissue destruction compared with ALT and is increasingly being adopted as the LT standard of care (Realini, 2008). SLT has been reported to reduce IOP effectively in eyes with OHT and OAG, as reports often suggest IOP reduction to be similar to topical prostaglandin analogues (Katz et al, 2012; Nagar et al, 2009; McAlinden 2014). This study is 1 of 2 phase 3 studies that will compare the IOP-lowering effects and safety profiles of Bimatoprost SR and SLT.

2. Study Objectives and Clinical Hypotheses

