- **Stage 2:** Bim SR 15 µg vs SLT; 2 administration cycles for patients who had not reached Week 32 prior to implementation of Amendment 2; and all patients enrolled under [Protocol Amendment 2](#)

Patients will receive a 360° administration of SLT in 1 eye on Day 1, and administration of Bim SR in the contralateral eye on Day 4 (Bim SR Cycle 1 Day 1), with a repeat administration of Bim SR at Week 16 (Bim SR Cycle 2 Day 1). Patients who were enrolled and reached Week 32 prior to implementation of Protocol Amendment 2 received a third administration of Bim SR at Week 32 (Bim SR Cycle 3 Day 1). Therefore, the planned number of treatment cycles for Stage 1 patients is 3, and the planned treatment cycles for Stage 2 patients is 2.

To mask the patient to the treatment assigned to each eye, on Day 1 a Sham SLT procedure will be performed in the eye to be administered Bim SR. A Sham Bim SR administration will be performed in the eye that underwent SLT on each Bim SR administration visit (Day 4 [Bim SR Cycle 1 Day 1] and Week 16 [Bim SR Cycle 2 Day 1]) (see Table 4-1). For brevity, the eye administered Bim SR will be referred to as the “Bim SR eye”, and the eye that underwent SLT will be referred to as the “SLT eye”.

Due to the paired-eye design of the study, the experimental units for treatment effects are individual eyes of each patient. Therefore, data summaries will primarily be done by randomized treatment (Bim SR and SLT). Where appropriate, data summaries at patient level will be provided.

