### 11.3.5 Specular Microscopy

**Endothelial Cell Density:** Endothelial cell density average (cells/mm^2) will be assessed using specular microscopy performed on the central cornea of each eye at Screening, Week 4, Week 12, Week 24, Week 40, and Week 52/Exit.

Endothelial cell density at baseline (Screening) and raw values and their changes from baseline will be summarized descriptively by visit for each eye.

In addition, the number and percentage of patient-eyes that showed following

- beyond 200 cells/mm^2 increase
- within 200 cells/mm^2 increase
- within 200 cells/mm^2 decrease
- ≥ 10% loss
- ≥ 20% loss
- ≥ 30% loss
- ≥ 40% loss
- ≥ 50% loss
- ≥ 10% and < 20% loss
- ≥ 20% and < 30% loss
- ≥ 30% and < 40% loss
- ≥ 40% and < 50% loss

in endothelial cell density change from baseline will be summarized by visit for each eye. Percent change from baseline is defined as:  $100 \times (\text{At Visit ECD} - \text{Baseline ECD}) / (\text{Baseline ECD})$  where ECD = endothelial cell density. For the ECD decrease, the worst ECD assessment within the given analysis visit window (or analysis cycle) including unscheduled visits will be summarized by visit and by analysis cycle. For the ECD increase, the maximum ECD assessment will be summarized by visit and by

analysis cycle. Listings for patients with 20% or more central corneal endothelia cell density (CECD) loss at any visit will be provided.

**Coefficient of Variation Average (CVAVE):** Coefficient of variation average of raw data and changes from baseline will be summarized descriptively by visit for each eye.

**Pleomorphism Average (HEXAVE):** Pleomorphism average of raw data and their changes from baseline will be summarized descriptively by visit for each eye.

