**Table 16-2 Visit windows for patients who only had Bim SR Cycles 1 and 2 implants**

Derived Visit	Target Visit Day	Visit Window
Baseline a	-1	≤ (SLT Date -1)
SLT/Sham SLT Administration Day 1	1	SLT Date
Bim SR Cycle 1 Day 1 b	Bim SR Cycle 1 Day 1	Bim SR Cycle 1 Day 1
Bim SR Cycle 1 Day 2 b	Bim SR Cycle 1 Day 1 + 1	Bim SR Cycle 1 Day 1 + 1
Week 4/Cycle 1 Week 4 b	25	[Bim SR Cycle 1 Day 1+ 2, 38]
Week 8/Cycle 1 Week 8 b	53	[39, 66]
Week 12/Cycle 1 Week 12 b	81	[67, 91]
Week 15/Cycle 1 Week 15 b	102	[92, Bim SR Cycle 2 Day1-Bim SR Cycle 1 Day 1]
Week 16/Bim SR Cycle 2 Day 1 c	1	Bim SR Cycle 2 Day 1
Cycle 2 Day 2 c	2	Bim SR Cycle 2 Day 1 + 1
Week 20/Cycle 2 Week 4 c	29	[Bim SR Cycle 2 Day 1+ 2, 42]
Week 24/Cycle 2 Week 8 c	57	[43, 70]
Week 28/Cycle 2 Week 12 c	85	[71, 95]
Week 31/Cycle 2 Week 15 c	106	[96, 109]
Week 32/Cycle 2 Week 16 c	113	[110, 126]
Week 36/Cycle 2 Week 20 c	141	[127, 154]
Week 40/Cycle 2 Week 24 c	169	[155, 182]
Week 44/Cycle 2 Week 28 c	197	[183, 207]
Week 47/Cycle 2 Week 31 c	218	[208, 235]
Week 52/Cycle 2 Week 36 c	253	>=236

a Relative to the date of the SLT treatment.

b Relative to the date of Bim SR 1st implant. If a patient did not receive the first Bim SR cycle, but treated in SLT at Day 1, Bim SR cycle 1 Day 1 will be determined as SLT+ 3 days.

c Relative to the date of Bim SR 2nd implant.

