**Table 16-3 Visit windows for patients who had Bim SR Cycle 1, 2 and 3 implants**

Derived Visit	Target Visit Day	Visit Window
Baseline a	-1	≤ (SLT Date -1)
SLT/Sham SLT Administration Day 1	1	SLT Date
Bim SR Cycle 1 Day 1 b	Bim SR Cycle 1 Day 1	Bim SR Cycle 1 Day 1
Bim SR Cycle 1 Day 2 b	Bim SR Cycle 1 Day 1 + 1	Bim SR Cycle 1 Day 1 + 1
Week 4/Cycle 1 Week 4 b	25	[Bim SR Cycle 1 Day 1+ 2, 38]
Week 8/Cycle 1 Week 8 b	53	[39, 66]
Week 12/Cycle 1 Week 12 b	81	[67, 91]
Week 15/Cycle 1 Week 15 b	102	[92, Bim SR Cycle 2 Day 1- Bim SR Cycle 1 Day 1]
Week 16/Bim SR Cycle 2 Day 1 c	1	Bim SR Cycle 2 Day 1
Cycle 2 Day 2 c	2	Bim SR Cycle 2 Day 1 + 1
Week 20/Cycle 2 Week 4 c	29	[Bim SR Cycle 2 Day 1+ 2, 42]
Week 24/Cycle 2 Week 8 c	57	[43, 70]
Week 28/Cycle 2 Week 12 c	85	[71, 95]
Week 31/Cycle 2 Week 15 c	106	[96, Bim SR Cycle 3 Day 1- Bim SR Cycle 2 Day1]
Week 32/Bim SR Cycle 3 Day 1 d	1	Bim SR Cycle 3 Day 1
Cycle 3 Day 2 d	2	Bim SR Cycle 3 Day 1 + 1
Week 36/Cycle 3 Week 4 d	29	[Bim SR Cycle 3 Day 1+ 2, 42]
Week 40/Cycle 3 Week 8 d	57	[43, 70]
Week 44/Cycle 3 Week 12 d	85	[71, 95]
Week 47/Cycle 3 Week 15 d	106	[96, 123]
Week 52/Cycle 3 Week 20 d	141	>=124

a Relative to the date of the SLT treatment.

b Relative to the date of Bim SR 1st implant. If a patient did not receive the first Bim SR cycle, but treated in SLT at Day 1, Bim SR cycle 1 Day 1 will be determined as SLT+ 3 days.

c Relative to the date of Bim SR 2nd implant.

d Relative to the date of Bim SR 3rd implant.

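### Analysis cycles differ in length by number of implants received, so crude by-cycle event rates and worst endothelial cell loss cannot compare first with repeat implants, and the distortion can go either way

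*SAP*

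**What the plan says.** SAP Section 11.0 starts Analysis Cycle 1 at SLT treatment on Day 1 and runs it "through the second Bim SR implant date", less one day. The second implant is planned for Week 16: SAP Section 4.0 describes SLT, then the first implant, "with a repeat administration of Bim SR at Week 16". If the second implant is not given, "all safety assessments through Week52/Exit visit/last study visit available will be included in analysis cycle1". Cycle 2 has the matching rule: without a third implant, "all safety assessments through Week52/Exit visit/last study visit available will be included in analysis cycle 2". Cycle 3 runs from the third implant to Week 52 or exit.

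SAP Section 11.1 reports ocular TEAEs, including corneal TEAEs of interest, as patient-eye incidences overall and by period. SAP Section 11.3.5 takes "the worst ECD assessment within the given analysis visit window (or analysis cycle) including unscheduled visits" and tabulates decreases both by visit and by analysis cycle. It also lists patients with 20% or more loss at any visit. Unless otherwise stated, the safety baseline is the last value before SLT, whatever the cycle.

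Under Protocol Sections 5.9.1.5 and 8.9, patients who miss the second implant, including those affected by Amendment 3, are followed to Week 52. SAP Section 6.1 removes the Amendment 3 group from the mITT population; the safety population in Section 6.3 keeps them.

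**The concern.** A crude percentage depends on how long each eye was watched. Here the length of a cycle depends on whether the next implant was given, so the by-cycle tables mix short and long windows in proportions that differ from cycle to cycle. The worst ECD value has the same problem, because a longer window also contains more readings from which to pick the worst.

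The comparison at stake is first implant against repeat implant. Protocol Section 1.3 explains why dosing at this strength stopped: "The discontinuation is based on the conclusion that corneal adverse events associated with repeat administrations" no longer had an acceptable benefit-risk balance. The protocol (Section 7.3.4) asks for adverse event tables by treatment cycle, and a reader interested in repeat dosing will naturally look along those columns. A difference between cycles, or its absence, could then be produced by window length alone.

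**Working it through.** The plan gives no by-cycle incidence to reproduce, and its sample-size figures concern IOP and play no part here. The window lengths can be checked.

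**Window lengths.** Implants are planned near the start, at Week 16 and, for Stage 1, at Week 32.
- Cycle 1: about 16 weeks if re-treated, about 52 if not; 52/16 = 3.25.
- Cycle 2: 52 − 16 = 36 weeks with two implants, matching the label "Week 52/Cycle 2 Week 36" in SAP Table 16-2; 32 − 16 = 16 weeks with three.
- Cycle 3: 52 − 32 = 20 weeks, matching "Week 52/Cycle 3 Week 20" in SAP Table 16-3.

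**Scheduled ECD readings** (Weeks 4, 12, 24, 40 and 52, SAP 11.3.5). Cycle 1 has 2 readings if re-treated and 5 if not. Cycle 2 has 3 with two implants and 1 with three.

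**Effect on crude incidence.** Let f be the share of patients with a single implant and s the share with three (Stage 1). From the planned numbers, s = 40/160 = 25%. Assumptions not in the documents: f ranged from 0 to 0.7; the same constant rate of 0.20 per eye-year in every cycle; full follow-up; and Cycle 2 percentages based on patients who received a second implant.

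Crude risk over t weeks: g(t) = 1 − exp(−0.20 × t/52), so g(16) = 6.0%, g(36) = 12.9%, g(52) = 18.1%.

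Cycle 1 = (1 − f) × g(16) + f × g(52).
Cycle 2 = [s × g(16) + (1 − s − f) × g(36)] / (1 − f).

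For s = 25%:

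| f | Mean Cycle 1, weeks | Mean Cycle 2, weeks | Crude Cycle 1 | Crude Cycle 2 | Ratio |
|---|---|---|---|---|---|
| 0 | 16.0 | 31.0 | 6.0% | 11.2% | 1.87 |
| 0.2 | 23.2 | 29.8 | 8.4% | 10.8% | 1.28 |
| 0.3 | 26.8 | 28.9 | 9.6% | 10.4% | 1.09 |
| 0.4 | 30.4 | 27.7 | 10.8% | 10.0% | 0.93 |
| 0.5 | 34.0 | 26.0 | 12.0% | 9.4% | 0.78 |
| 0.7 | 41.2 | 19.3 | 14.5% | 7.1% | 0.49 |

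The true ratio is 1.00 in every row.

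**Where the direction changes.** Mean Cycle 1 length is 16 + 36f weeks. With s = 25% it equals mean Cycle 2 length when 36f² − 56f + 15 = 0, that is f = 0.34. With no Stage 1 patients, 16 + 36f = 36 gives f = 0.56. Below these shares Cycle 2 is the longer window and a repeat-implant effect is exaggerated. Above them it can be masked: with s = 25%, a true ratio of 1.30 at f = 0.5, or 1.59 at f = 0.6, would look like no difference.

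**Effect of the number of ECD readings.** Assume no true loss, an error SD of 5% per reading and one baseline reading shared by all later ones (simulated). The chance that the worst change is a loss of 10% or more is about 8% with 1 reading, 13% with 2, 18% with 3 and 24% with 5. The 5% is an illustration; at 4% the figures for 2 and 5 readings are 7% and 13%, at 6% they are 20% and 33%.

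**Check of the remedy.** Under the same equal rates, events per eye-year, or incidence in a common 16-week window (6.0% in each), return a ratio of 1.00 for any f.

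**The case against.** Several points on the other side are sound.

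- Both eyes of a patient share each cycle window, so the SLT eye is a time-matched control. The comparison of Bim SR with SLT within a cycle is not distorted.
- ECD is better protected than adverse events. The by-visit tables and the listing of 20% or more loss do not depend on cycle length, and the common pre-SLT baseline makes later-cycle loss cumulative, which works against hiding it.
- The constant rate is an assumption. Protocol Section 1.2.3 says most adverse events in the phase 1/2 study arose within 2 days of administration, and SAP Section 11.1 already separates TEAEs within two days from later ones. For events that cluster at the procedure, window length matters much less; the problem lies with events that keep accruing.
- Table specifications are in a separate document (SAP Section 4.0), so an exposure-adjusted table may exist there.
- The decision to stop dosing rested on data from completed and ongoing studies. Nothing says it depended on these tables.

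These points limit the finding but do not supply a valid comparison of first with repeat implants for later-onset ocular and corneal TEAEs.

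A reader might also infer that the open-ended Cycle 1 necessarily overstates first-implant risk and so hides a repeat-dose signal. The documents do not support that. Cycle 2 is open-ended too, and at the planned stage sizes with everyone re-treated it is the longer window (31 against 16 weeks on average), which would exaggerate such a signal. The share of single-implant patients decides the direction, and it is not given.

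**Conclusion.** The point holds as a matter of comparability, without a fixed direction. Followed exactly, the SAP produces by-cycle TEAE incidences and worst-in-cycle ECD losses over windows of 16 or 52, 16 or 36, and 20 weeks, depending on implants received. With no true difference, the crude Cycle 2/Cycle 1 ratio could lie anywhere from about 1.87 to about 0.49. That range rests on an assumed constant 0.20 events per eye-year, a 25% Stage 1 share, full follow-up and a single-implant share between 0 and 70%.

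This is a modest reporting weakness. Primary efficacy, sample size and the between-eye safety comparison are untouched, and the ECD part is softened by the by-visit tables and the listing.

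**What to change.** Keep the cycle definitions and the planned by-cycle tables, and add three outputs:

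1. Ocular and corneal TEAEs per eye-year at risk, by cycle and by eye.
2. The by-cycle corneal TEAE table limited to a common window of 16 weeks after each implant (or the matching sham in the SLT eye), ending the day before the next implant if that is sooner.
3. The by-visit ECD summaries split by number of implants received.

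The third takes the place of a worst-ECD table limited to 16 weeks. That table would have 2 scheduled readings after the first implant (Weeks 4 and 12) and only 1 after each repeat (Week 24, then Week 40), so unequal numbers of readings would return.

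The cost is a few descriptive tables from data already collected. The fixed window omits late events, so it supplements the full-cycle tables and does not replace them. None of the additions removes selection: patients who were not re-treated because of an adverse event or rescue stay in Cycle 1, and a footnote should say so.
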